13.2.2. Assessment Windows for PK Concentration Data

PK data will be presented in data listings according to planned nominal visits (i.e. as collected in the eCRF), without additional assignment to assessment windows.

13.2.3. Assessment Windows for Pregnancy Data

Pregnancy visits will be assigned in accordance with the derivations listed in Table 1 to Table 5 as appropriate for the relevant data. Post-partum visit data will be labelled based on the nominal timepoint

13.3. Appendix 3: Study Phases

13.3.1. Study Phases

Participants are considered to have entered the Extension phase if they have a Month 14 visit. They are considered to enter the LTFU period if they have a post-treatment, non-bridging ART start date or LTFU visit entered in the CRF, including LTFU withdrawal.

Participants are considered to have completed the Intervention Phase upon successful completion of the Month 12 visit without discontinuing from study treatment. Extension Phase completion is defined as successful transition to commercial product whenever it becomes available by attending a Safety Follow-up visit and not discontinuing treatment.

Table 6 Participant Phase Entry and Conclusion Windows

Phase	Qualifying Entry Timepoint	Qualifying Conclusion Timepoint
Intervention Phase	First CAB + RPV dose date	Month 14 visit date; or Safety Follow-up visit date (if transitioned to commercial product); or LTFU ART start date (if discontinued from treatment after receiving at least one dose of CAB/RPV LA)
Extension Phase	Month 14 visit date	Safety Follow-up visit date (if transitioned to commercial product); or LTFU ART start date (if discontinued from treatment after receiving at least one dose of CAB/RPV LA)
LTFU Phase	LTFU ART start date or LTFU Visit date existence	LTFU Month 12 visit date

AEs will be assigned to study phases as defined in Table 7. Laboratory data (efficacy, safety, and virology), HIV associated Conditions, health outcomes assessments, and vital signs will be assigned to study phases as defined in Table 8.

Assessments/events are assigned to study phases sequentially, starting from the top of each table.

Table 7 Study Phases for AEs

Study Phase	Definition
Screen	Date < Intervention Phase Treatment Start Date
Intervention Phase	
For subjects continuing into the Extension Phase: Intervention Phase Treatment Start Date ≤ Date < Date of Nominal Month 14 Visit
 
For subjects not continuing into the Extension Phase: Intervention Phase Treatment Start Date ≤ Date < LTFU ART Start Date^[a]

Study Phase	Definition
	
For subjects transitioning to commercial product without discontinuing or entering Extension: Intervention Phase Treatment Start Date ≤ Date ≤ Safety Follow-up visit date
 
For AEs leading to treatment withdrawal with start date equal to the LTFU ART Start Date, Intervention Phase instead of Long-term Follow-up Phase will be assigned.

Extension Phase	
For subjects transitioning to commercial product: Date of Nominal Month 14 Injection ≤ Date ≤ Safety Follow-up visit date
 
For subjects not transitioning to commercial product: Date of Nominal Month 14 Injection ≤ Date < LTFU ART Start Date ^[a]
 
For AEs leading to treatment withdrawal with start date equal to the LTFU ART Start Date, Extension Phase instead of Long-Term Follow-up Phase will be assigned.

Long Term Follow-Up	
For subjects who receive at least one CAB/RPV injection and permanently discontinue study treatment: AE Start Date ≥ LTFU ART Start Date

AEs with completely missing start date:
 
 • If AE end date is ≤ Intervention Phase Treatment Start Date, then assign to Screening Phase; • Else if AE end date is completely missing or Intervention Phase Treatment Start Date < AE end date ≤ Date of Nominal Month 14 Injection, then assign to Intervention Phase; • Else if AE end date > Date of Nominal Month 14 Injection, then assign to Extension Phase. 	

- Date=AE Start Date
- [a] If participants have missing LTFU ART start date, only the lower bound will be considered in the derivation.

Table 8 Study Phases for Laboratory, Vital Signs, HIV-1 Associated Conditions, and Protocol Deviation Data

Study Phase	Definition
Screen	Date ≤ Study Treatment Start Date
Intervention Phase	
For subjects continuing into the Extension Phase: Intervention Phase Treatment Start Date < Date < Date of Nominal Month 14 Visit
 
For subjects not continuing into the Extension Phase: Intervention Phase Treatment Start Date < Date ≤ LTFU ART Start Date ^[a]
 
For subjects transitioning to commercial product without discontinuing or entering Extension: Intervention Phase Treatment Start Date < Date ≤ Safety Follow-up visit date

Extension Phase	
For subjects continuing into Extension Phase: Date of Nominal Month 14 Visit ≤ Date ≤ LTFU ART Start Date ^[a] or Safety Follow-up visit date

Long Term Follow-Up	
For subjects who receive at least one CAB/RPV injection and permanently discontinue study treatment: Assessment Date > LTFU ART Start Date

- Date = start or assessment date
- [a] If participants have missing LTFU ART start date, only the lower bound will be considered in the derivation.

Study phase of discontinuation will be determined according to Table 9.

Table 9 Study Phases for Study Conclusion/IP Discontinuation

Study Phase	Definition
Intervention Phase	Discontinuation Date is not missing, and no assessments collected at any extension phase nominal visits (i.e. Month 14, Month 16, Month 18 etc.).
Extension Phase	Discontinuation Date is not missing, and assessments collected at any extension phase nominal visits (i.e. Month 14, Month 16, Month 18 etc.).

- Discontinuation Date = date of failure to complete study/date of IP discontinuation

Medication use will be classified as prior and concomitant with study treatment according to Table 10, noting that a medication can be assigned as “taken” during more than one study phase.

Table 10 Study Phases for Non-ART Medications/ART Medications

	Definition
Prior	Medication Taken < Intervention Treatment Start Date
Concomitant during Intervention Phase	
For subjects continuing into Extension Phase: Intervention Treatment Start Date^[a] ≤ Medication Taken < Date of Nominal Month 14 Visit
 
For subjects not continuing into Extension Phase^[b]: Intervention Treatment Start Date^[a] ≤ Medication Taken < LTFU ART Start Date
 
For subjects transitioning to commercial product without discontinuing or entering Extension: Intervention Phase Treatment Start Date ≤ Medication Taken ≤ Safety Follow-up visit date

Concomitant during Extension Phase	
For subjects transitioning to commercial product: Date of Nominal Month 14 Injection ≤ Medication Taken ≤ Safety Follow-up visit date
 
For subjects not transitioning to commercial product: Date of Nominal Month 14 Injection ≤ Medication Taken < LTFU ART Start Date

Received during Long-term Follow-up	
For subjects who received at least one CAB and/or RPV injection and have started LTFU ART: Medication Taken ≥ LTFU ART Start Date

NOTES:

- Please refer to [Appendix 6: Reporting Standards for Missing Data](#) for handling of missing and partial dates for medications. Use the rules in this table if medication date is completely missing.
 - The ART medication stopped on start date of Intervention treatment will be considered a prior medication and will not be considered concomitant during the Intervention phase. If the stop date of ART medication is completely missing and this medication is recorded in eCRF as prior, it will be considered a prior medication and will not be considered concomitant during the intervention phase.
 - If subjects have missing LTFU ART start date, only the lower bound will be considered in the derivation.

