4.3.4. LTFU Phase – Following the IM Regimen Only

Any participant who receives *at least one* dose of CAB LA and/or RPV LA and discontinues the CAB LA + RPV LA regimen for any reason before CAB LA + RPV LA marketed product is locally available must enter the LTFU Phase. Participants must remain on suppressive HAART for at least 52 weeks after the last dose of CAB LA and/or RPV LA in order to prevent selective pressure on HIV during the period of declining drug exposures and the potential for selection of resistant mutants.

• Where the CAB LA + RPV LA Marketed Product is Locally Available

Only the participants that discontinue the CAB LA + RPV LA regimen for **safety-related reasons** included in Section 7, must enter the LTFU Phase. Participants must remain on suppressive highly active antiretroviral therapy (HAART) for at least 52 weeks after the last dose of CAB LA and/or RPV LA in order to prevent selective pressure on HIV during the period of declining drug exposures and the potential for selection of resistant mutants.

NOTE: Participants who transition to CAB+RPV LA, marketed product or alternative HAART (except due to safety-related reasons) do not need to enter the LTFU Phase.

Investigators must discuss the choice of the follow-up HAART regimen with the Medical Monitor prior to initiating the new regimen with the participant. HAART therapy should be initiated within one month (- 7 days) after the last dose if interruption is prior to Dose 2 and within 2 months (± 7 days) after the last injection if interruption is following Dose 2, however if withdrawn due to virologic failure, HAART should be initiated as soon as virologic failure is confirmed. Discuss with Medical Monitor. The Long-Term Follow Up period (LTFU) will begin the day of the last CAB LA and/or RPV LA dose and continue for 52 weeks.

Marketed product locally available	Subject WD due to safety- related reasons	LTFU phase required?
No	Yes No	Yes
Yes	Yes	Yes
	No	No, but Safety FU visit required to assess potential safety issues occurred after the last injection see Section 4.5.1.2 Safety Follow-up Visit.

Long term Follow up phase requirement

Participants entering the LTFU phase will not complete a Withdrawal visit but will instead move directly into the LTFU Phase as per the schedule of activities. In addition, for participants who withdraw during the LTFU Phase, the final visit will be considered the study withdrawal visit.

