4.5.1.2. Patient Study Participants

The investigator is responsible for ensuring that consideration has been given to the poststudy care of the patient study participant's medical condition.

Patient study participants are considered to have completed the study if they have completed all study visits and assessments up to and including Dose 7 (Month 12).

Post Dose 7 (Month 12), they should remain on study (Extension Phase) until; Commercial supplies of the CAB LA + RPV LA regimen become locally available, they are required to initiate alternate antiretroviral therapy at the discretion of their HIV care provider, or until development of CAB LA + RPV LA is terminated.

Until meeting the definition for study completion, participants will continue in the study until the participant no longer derives clinical benefit or the participant meets a protocoldefined reason for discontinuation.

Following commercial availability, patient study participants will exit the study and transition to commercial supplies of CAB LA + RPV LA, or alternate antiretroviral therapy at the discretion of their HIV care provider.

Safety Follow-up Visit

A safety follow-up visit is required for subjects completing the study when commercial supplies become available, (participant may or may not be transitioning to CAB + RPV LA marketed product). It should be conducted approximately 2-4 weeks after the last dose of IP to assess HIV associated conditions, AEs, Concomitant medications, ISR AEs after the last injection and the plan to transition to marketed product. This visit may be conducted by telephone. Ensure relevant eCRF forms (including the Study Conclusion form) are updated / completed.

Participants who withdraw from CAB LA + RPV LA and go into the LTFU phase will be considered to have prematurely withdrawn from the study intervention.

Follow-Up visits are not required for successful completion of the study.

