Patient participants in CARISEL who successfully complete the study (Dose 7), without meeting study-defined withdrawal criteria, will be given the option to continue to receive CAB LA + RPV LA, administered Q2M in the Extension Phase until the study treatment is either locally approved and commercially available (including through local public/government health sectors), the participant no longer derives clinical benefit, the participant meets a protocol-defined reason for discontinuation or until development of either CAB LA + RPV LA Q2M is terminated. Alternatively, participants can choose to complete study participation and enter the 52-week LTFU Phase of the study.

Any participant who receives at least one dose of CAB LA and/or RPV LA and discontinues the CAB LA + RPV LA regimen for any reason will enter a 52-week LTFU Phase. Those participants must remain on suppressive highly active antiretroviral therapy (HAART) for at least 52 weeks after the last dose of CAB LA and/or RPV LA.

There are two arms for the providers (arm-e and arm-s) which contain different levels and type of support for the implementation of the HIV Regimen. Cluster randomization will be used to randomize sites in each country to either arm-e or arm-s.

Overview of Study Design and Key Features	

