
Study Day
 
 • The Study Day of an event (e.g., lab assessment, vital sign, ECG, start date of AE or HIV associated condition) will be derived as the number of days between the date of the event and the Intervention Phase treatment start date as follows: 
 ○ If date of event \geq start date of study treatment, then 
 ▪ Study Day = Date of Event - Intervention Phase Treatment Start Date +1 ○ If date of event $<$ start date of study treatment, then 
 ▪ Study Day = Date of Event - Intervention Phase Treatment Start Date • Note that the start date of intervention phase study treatment is on Study Day 1 and the day before this is Study Day -1; i.e., there is no Study Day 0.

Long Term Follow-up Study Day

 Participants are considered to have entered LTFU if they have a post-treatment, non-bridging ART medication start date or a LTFU visit entered in the CRF. The Long-Term Follow Up (LTFU) Study Day of an event (e.g., lab assessment, start date of AE or HIV associated condition) will be derived as the number of days between the date of the event and the end of IP treatment [i.e. min(LTFU ART Start Date, max>Last IM Injection Date, Last Oral Bridging End Date)] as follows: 
 If the date of event falls in Long-term Follow up phase, then 
 LTFU Study Day = Date of event - min(LTFU ART Start Date, max>Last IM Injection Date, Last Oral Bridging End Date) + 1
Study Treatment

 Refers to CAB+RPV oral lead-in, CAB + RPV oral bridging, SOC bridging, CAB LA + RPV LA
Change from Baseline

 Post-Dose Visit Value – Baseline 
 Unless otherwise specified, the baseline definitions specified in Section 5.2 will be used for derivations for endpoints / parameters.

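### The SAP counts any recorded post-treatment ART start as entry into long-term follow-up, although the protocol exempts non-safety leavers on alternative HAART once product is locally available

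*SAP*

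**What the plan says.** **SAP.** Section 13.3.1 on LTFU entry: "They are considered to enter the LTFU period if they have a post-treatment, non-bridging ART start date or LTFU visit entered in the CRF". Section 13.5.1 repeats it: "Participants are considered to have entered LTFU if they have a post-treatment, non-bridging ART medication start date or a LTFU visit entered in the CRF". In Table 6 the LTFU entry point is "LTFU ART start date or LTFU Visit date existence" and the conclusion point is "LTFU Month 12 visit date". The footnote to the disposition shell DISP_T1 counts a subject as entered after at least one injection and a start of LTFU ART. On the phase before it, 13.3.1 says: "Extension Phase completion is defined as successful transition to commercial product whenever it becomes available", shown by attending the Safety Follow-up visit and not discontinuing treatment. The design summary in 2.3 still says that anyone who has had an injection and "discontinues the CAB LA + RPV LA regimen for any reason will enter a 52-week LTFU Phase".

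**Protocol.** Section 4.3.4 carries an exemption: "Participants who transition to CAB+RPV LA, marketed product or alternative HAART (except due to safety-related reasons) do not need to enter the LTFU Phase". Its requirement table gives the same answer where product is available and the reason is not safety: no LTFU, but a Safety Follow-up visit. Section 4.5.1.2 treats both routes as leaving the study: "patient study participants will exit the study and transition to commercial supplies of CAB LA + RPV LA, or alternate antiretroviral therapy". It defines study completion as having done all visits and assessments through Dose 7.

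**The concern.** The current protocol has two exempt ways out after local availability: marketed CAB+RPV LA, and another regimen chosen for a non-safety reason. The SAP carries only the first. Its LTFU entry rule asks neither why treatment ended nor whether product was available. Its completion definition and its Safety Follow-up phase end (Tables 6, 7 and 10) name only the move to commercial product.

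This does not read as a deliberate departure. SAP Amendment 1 was written against protocol amendment 02 and says that it clarifies LTFU entry and the transition to commercial product. SAP 2.1, which lists changes from the protocol analysis, mentions only the replacement of the ITT-E population.

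At stake are correct disposition counts by phase and complete adverse event summaries. The route is foreseeable: protocol 2.3.2 describes the regimen as recently approved in the EU, and 4.2.6.4 expects study start to overlap with local availability in Germany.

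**Working it through.** No power, alpha or event figure is involved, so the check is a rule trace. Take a participant who has had Dose 7 and is in Extension, with product locally available. The participant leaves for alternative HAART for a non-safety reason, has the Safety Follow-up visit, and has a post-treatment, non-bridging ART start date in the CRF.

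| Question | Protocol 4.3.4, 4.5.1.2 | SAP |
|---|---|---|
| Study completed? | Yes, through Dose 7 | Intervention Phase completed at Month 12 (13.3.1) |
| Extension completed? | Leaving at availability is a planned exit | Definition not met: only commercial transition qualifies |
| LTFU entered? | Not required | Yes, on the ART start alone (13.3.1, Table 6, 13.5.1) |
| LTFU completed or withdrawn? | Not applicable | Taken from the Study Conclusion form (Table 1.3 note, DISP_T1 footnote) |
| In LTFU population? | Not applicable | No: Section 4 requires an LTFU clinic visit |

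**Disposition.** Table 1.3 is run on the Safety population, so the clinic-visit requirement of the LTFU population does not keep this participant out of the LTFU Entered row.

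**Adverse events.**
1. Table 7 ends Extension before the LTFU ART start for anyone not moving to commercial product. After an injection and permanent discontinuation, it assigns an event starting on or after the ART start to LTFU. The one carve-out is an event leading to withdrawal that starts on the ART start date itself.
2. SAP 8 and 13.12 present the main summaries for the Safety population across Intervention and Extension.
3. The LTFU event tables (3.14, 3.21, 3.29, 3.34) use the LTFU population, which excludes this participant.
4. Such an event therefore belongs to neither set. It may still show as a count in the phase overview (Table 3.9, Safety population) and, if serious or leading to discontinuation, in Listings 22 and 23.

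**Laboratory data and HIV-associated conditions.** Table 8 differs. Its Extension row ends at the LTFU ART start or the Safety Follow-up date, with no commercial-product condition. Only its Intervention rows restrict the Safety Follow-up end to commercial transition.

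**When the rule fires.** The Safety Follow-up visit is about 2 to 4 weeks after the last dose, or 2 × 7 = 14 to 4 × 7 = 28 days. HAART after Dose 2 is due within two months ± 7 days, so up to about 2 × 30.4 + 7 = 67.8, roughly 68 days. The visit may thus precede the ART start. Events before that start keep the Intervention or Extension phase. If no ART start is recorded, the LTFU entry rule does not fire, and the footnotes to Tables 7 and 8 keep only the lower bound, so data stay in the earlier phase. Table 6 then offers this participant no conclusion date at all.

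**The case against.** The strongest reply is that the affected group is small and the analyses largely protected. It takes local availability, a non-safety exit, a regimen other than marketed product, and an ART start that reaches the CRF. Protocol 6.1 specifies recording the selected HAART for participants entering LTFU, and an exempt leaver may be gone before starting it. The LTFU population excludes people without an LTFU clinic visit, so LTFU tables do not gain these participants. Intervention completion does not depend on commercial transition, and Intervention/Extension status in Table 1.3 comes from the treatment discontinuation form. SAP 2.3 is a design summary, not a derivation rule.

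All of that stands, and it limits the reach of the point. It does not supply the missing exemption: no SAP section excludes these leavers from LTFU entry or gives them an exit in Tables 6, 7 and 10. The LTFU population definition is also what leaves their later adverse events without a table.

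Three stronger readings are tempting and unsupported:
- **That exempt leavers would appear as LTFU entrants who never finished, depressing apparent retention.** LTFU status comes from the Study Conclusion form. A false LTFU completion is as possible as a false withdrawal, and the documents do not settle which.
- **That all data from the Safety Follow-up visit fall in the wrong phase.** Table 8 has no commercial-product condition for Extension, and the visit may come before the ART start.
- **That every exempt leaver is a study completer.** Where product is already available, some may leave before Dose 7.

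**Conclusion.** The point holds in a limited form. The SAP rule for LTFU entry conflicts with protocol 4.3.4 and 4.5.1.2 for non-safety leavers on alternative HAART after local availability. Three consequences follow from the text:
- a false LTFU Entered count in Table 1.3;
- an Extension-completion definition that these participants cannot meet;
- adverse events on or after the ART start that can drop out of both the Intervention/Extension and the LTFU-population event tables.

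The first and third require a recorded ART start; the second applies only to those in Extension. The size cannot be computed, because the documents give neither the number who leave for another regimen nor the number with an ART start recorded. Any percentage for LTFU retention would be guesswork. No effect on the primary staff-participant endpoint or on the Month 12 Snapshot result has been shown. It is a correction to make in the phase derivations, not a threat to the trial's main conclusions.

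**What to change.** 1. Define LTFU entry by an actual LTFU visit or LTFU record (including LTFU withdrawal), or by the protocol 4.3.4 criteria of local availability and safety-related reason. An ART start alone should not be enough. Criteria based on 4.3.4 also capture people required to enter LTFU who drop out before their first visit.
2. Add an exit to alternative ART after local availability, with the Safety Follow-up visit as phase end, to Tables 6, 7 and 10 and to the Intervention rows of Table 8.
3. Align Extension completion in 13.3.1 with protocol 4.5.1.2, so that leaving at local availability by either exempt route is handled the same way.
4. Carry the new entry rule into 13.5.1 and the DISP_T1 footnote, and update SAP 2.3 to the current protocol.

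The cost is SAP wording and reprogramming of the phase derivations. Where local availability or the reason for leaving is not already in the analysis data, the first option (LTFU visit or record) avoids needing it.
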